8.1.1 Definition of Adverse Events (AE)

An **adverse event** (AE) is any symptom, sign, illness or experience that develops or worsens in severity during the course of the study. Intercurrent illnesses or injuries should be regarded as adverse events. Abnormal results of diagnostic procedures are considered to be adverse events if the abnormality:

- results in study withdrawal
- is associated with a serious adverse event
- is associated with clinical signs or symptoms
- leads to additional treatment or to further diagnostic tests
- is considered by the investigator to be of clinical significance

8.1.2 Definition of Serious Adverse Events (SAE)

Serious Adverse Event

Adverse events are classified as serious or non-serious. A **serious adverse event** is any AE that is:

- fatal
- life-threatening
- requires or prolongs hospital stay
- results in persistent or significant disability or incapacity
- a congenital anomaly or birth defect
- an important medical event

Important medical events are those that may not be immediately life threatening, but are clearly of major clinical significance. They may jeopardize the subject, and may require intervention to prevent one of the other serious outcomes noted above. For example, drug overdose or abuse, a seizure that did not result in in-patient hospitalization, or intensive treatment of bronchospasm in an emergency department would typically be considered serious.

All adverse events that do not meet any of the criteria for serious should be regarded as **non-serious adverse events**.

8.1.3 Definition of Unanticipated Problems (UP)

Unanticipated Problems Involving Risk to Subjects or Others

Any incident, experience, or outcome that meets all of the following criteria:

- Unexpected in nature, severity, or frequency (i.e. not described in study-related documents such as the IRB-approved protocol or consent form, the investigators brochure, etc)
- Related or possibly related to participation in the research (i.e. possibly related means there is a reasonable possibility that the incident experience, or outcome may have been caused by the procedures involved in the research)
- Suggests that the research places subjects or others at greater risk of harm (including physical, psychological, economic, or social harm).

This definition could include an unanticipated adverse device effect, any serious adverse effect on health or safety or any life-threatening problem or death caused by, or associated with, a device, if that effect, problem, or death was not previously identified in nature, severity, or degree of incidence in the investigational plan or application (including a supplementary plan or application), or any other unanticipated serious problem associated with a device that relates to the rights, safety, or welfare of subjects (21 CFR 812.3(s)).

8.2 Classification of an Adverse Event

8.2.1 Severity of Event

For AEs not included in the protocol defined grading system, the following guidelines will be used to describe severity.

- **Mild** – Events require minimal or no treatment and do not interfere with the participant's daily activities.
- **Moderate** – Events result in a low level of inconvenience or concern with the therapeutic measures. Moderate events may cause some interference with functioning.
- **Severe** – Events interrupt a participant's usual daily activity and may require systemic drug therapy or other treatment. Severe events are usually potentially life-threatening or incapacitating.

8.2.2 Relationship to Study Agent

The clinician's assessment of an AE's relationship to study agent (drug, biologic, device) is part of the documentation process, but it is not a factor in determining what is or is not reported in the study. If there is any doubt as to whether a clinical observation is an AE, the event should be reported. All AEs must have their relationship to study agent assessed. In a clinical trial, the study product must always be suspect. To help assess, the following guidelines are used.

- **Related** – *The AE is known to occur with the study agent, there is a reasonable possibility that the study agent caused the AE, or there is a temporal relationship between the study agent and event. Reasonable possibility means that there is evidence to suggest a causal relationship between the study agent and the AE.*
- **Not Related** – *There is not a reasonable possibility that the administration of the study agent caused the event, there is no temporal relationship between the study agent and event onset, or an alternate etiology has been established.*

8.2.3 Expectedness

[name] will be responsible for determining whether an AE is expected or unexpected. An AE will be considered unexpected if the nature, severity, or frequency of the event is not consistent with the risk information previously described for the study agent.

8.3 Time Period and Frequency for Event Assessment and Follow-Up

The occurrence of an AE or SAE may come to the attention of study personnel during study visits and interviews of a study participant presenting for medical care, or upon review by a study monitor. All AEs including local and systemic reactions not meeting the criteria for SAEs will be captured on the appropriate RF. Information to be collected includes event description, time of onset, clinician's assessment of severity, relationship to study product

(assessed only by those with the training and authority to make a diagnosis), and time of resolution/stabilization of the event. All AEs occurring while on study must be documented appropriately regardless of relationship. All AEs will be followed to adequate resolution.

Any medical condition that is present at the time that the participant is screened will be considered as baseline and not reported as an AE. However, if the study participant's condition deteriorates at any time during the study, it will be recorded as an AE. UPs will be recorded in the data collection system throughout the study.

Changes in the severity of an AE will be documented to allow an assessment of the duration of the event at each level of severity to be performed. AEs characterized as intermittent require documentation of onset and duration of each episode.

The PI will record all reportable events with start dates occurring any time after informed consent is obtained until 7 (for non-serious AEs) or 30 days (for SAEs) after the last day of study participation. At each study visit, the investigator will inquire about the occurrence of AE/SAEs since the last visit. Events will be followed for outcome information until resolution or stabilization.

All unresolved adverse events should be followed by the investigator until the events are resolved, the subject is lost to follow-up, or the adverse event is otherwise explained. At the last scheduled visit, the investigator should instruct each subject to report any subsequent event(s) that the subject, or the subject's personal physician, believes might reasonably be related to participation in this study. The investigator should notify the study sponsor of any death or adverse event occurring at any time after a subject has discontinued or terminated study participation that may reasonably be related to this study. The sponsor should also be notified if the investigator should become aware of the development of cancer or of a congenital anomaly in a subsequently conceived offspring of a subject that has participated in this study.

8.4 Reporting Procedures – Notifying the IRB

8.4.1 Adverse Event Reporting

At each contact with the subject, the investigator must seek information on adverse events by specific questioning and, as appropriate, by examination. Information on all adverse events should be recorded immediately in the source document, and also in the appropriate adverse event module of the case report form (CRF). All clearly related signs, symptoms, and abnormal diagnostic procedures results should be recorded in the source document, though should be grouped under one diagnosis.

All adverse events occurring during the study period must be recorded. The clinical course of each event should be followed until resolution, stabilization, or until it has been determined that the study treatment or participation is not the cause. Serious adverse events that are still ongoing at the end of the study period must be followed up to determine the final outcome. Any serious adverse event that occurs after the study period and is considered to be possibly related to study participation should be recorded and reported immediately.

8.4.2 Serious Adverse Event Reporting

Investigators will conform to the adverse event reporting timelines, formats and requirements of the various entities to which they are responsible, but at a minimum those events that must be reported are those that are:

- related to study participation,
- unexpected, and
- serious or involve risks to subjects or others.

For Narrative Reports of Safety Events

If the report is supplied as a narrative, the minimum necessary information to be provided at the time of the initial report includes:

- Study identifier
- Study Center
- Subject number
- A description of the event
- Date of onset
- Current status
- Whether study treatment was discontinued
- The reason why the event is classified as serious
- Investigator assessment of the association between the event and study treatment

8.4.3 Unanticipated Problem Reporting

In the event of a UP, the study investigators will send a UP report to the IRB. The UP report will include the following information:

- Protocol identifying information: protocol title and number, PI's name, and the IRB project number;
- A detailed description of the event, incident, experience, or outcome;
- An explanation of the basis for determining that the event, incident, experience, or outcome represents an UP;
- A description of any changes to the protocol or other corrective actions that have been taken or are proposed in response to the UP.

To satisfy the requirement for prompt reporting, UPs will be reported using the following timeline:

- UPs that are SAEs will be reported to the IRB within one week of the investigator becoming aware of the event.
- Any other UP will be reported to the IRB within one week of the investigator becoming aware of the problem.
- All UPs should be reported to appropriate institutional officials (as required by an institution's written reporting procedures), the supporting agency head (or designee), and OHRP within one week of the IR's receipt of the report of the problem from the investigator.

8.5 Reporting Procedures – Notifying the Study Sponsor

The study investigators will complete a SAE Form within the following timelines:

- All deaths and immediately life-threatening events, whether related or unrelated, will be recorded on the SAE Form and submitted to the study sponsor within 24 hours of site awareness. See Section 1, Key Roles for contact information.
- Other SAEs regardless of relationship will be submitted to the study sponsor within 72 hours of site awareness.

All SAEs will be followed until satisfactory resolution or until the site investigator deems the event to be chronic or the adherence to be stable. Other supporting documentation of the event may be requested by the study sponsor and should be provided as soon as possible.

As a follow-up to the initial report, within the following 48 hours of awareness of the event, the investigator shall provide further information, as applicable, on the unanticipated event or the unanticipated problem in the form of a written narrative. This should include a copy of the completed Unanticipated Problem form, and any other diagnostic information that will assist the understanding of the event. Significant new information on ongoing unanticipated adverse effects shall be provided promptly to the study sponsor.

The study investigator shall complete an Unanticipated Adverse Device Effect Form and submit to the study sponsor and to the reviewing IRB as soon as possible, but in no event later than 10 working days after the investigator first learns of the effect. The study sponsor contact information is provided in Section 1, Key Roles.

As a follow-up to the initial report, within the following 48 hours of awareness of the event, the investigator shall provide further information, as applicable, on the unanticipated event or the unanticipated problem in the form of a written narrative. This should include a copy of the completed Unanticipated Problem form, and any other diagnostic information that will assist the understanding of the event. Significant new information on ongoing unanticipated adverse effects shall be provided promptly to the study sponsor.

The study sponsor is responsible for conducting an evaluation of an unanticipated adverse device effect and shall report the results of such evaluation to FDA and to all reviewing IRBs and participating investigators within 10 working days after the sponsor first receives notice of the effect. Thereafter the sponsor shall submit such additional reports concerning the effect as FDA requests.

8.6 Reporting Procedures – Notifying the FDA

The following describes the IDE safety reporting requirements by timeline for reporting and associated type of event:

- Within 5 working days (via written report)
- Protocol deviation to protect the life of the subject in emergency
- Withdrawal of IRB approval
- Lack of informed consent
- Within 10 working days (via telephone or facsimile report)

Any study event that is:

- associated with the use of the study device, and
- unanticipated, regardless of the seriousness of the event.

Additional reporting requirements

Sponsors are also required to identify in safety reports all previous reports concerning similar adverse events and to analyze the significance of the current event in light of the previous reports.

Reporting Process

Adverse events will be in a narrative format. As such, the minimum information to be supplied is noted above at the beginning of section this section. The contact information for submitting safety reports is noted below:

Reports will be sent via the FDA.gov website using the FDA Form 3500

8.7 Study Halting Rules

No halting rules will be used. The study poses no more than minimal risk to participants. Participants are free to withdraw at any time for any reason.

8.8 Safety Oversight

It is the responsibility of the Principal Investigator to oversee the safety of the study at his/her site. This safety monitoring will include careful assessment and appropriate reporting of adverse events as noted above, as well as the construction and implementation of a site data and safety-monitoring plan (DSMP). Medical monitoring will include a regular assessment of the number and type of serious adverse events.

Data Safety Monitoring Plan

Safety oversight will be under the direction of the study PI, [name] and the study investigator, [name]. The DSMP members will meet twice, once at the 6-month time point and again at the 12 month time point, to assess safety data on each arm of the study. Safety will be assessed by quantifying the number, percentage, magnitude, and frequency of:

- Headache
- Dizziness
- Arm soft-tissue discomfort
- Complaints (non-specific to anticipated risks)
- Breaches of confidentiality

There are no halting rules for this study. A summary of the outcomes of these safety reviews along with accumulated adverse events and deviations will be submitted to the IRB as part of an annual progress report at the time of the Continuing Review submission.

9 Clinical Monitoring

Clinical site monitoring is conducted to ensure that the rights and well-being of human subjects are protected, that the reported trial data are accurate, complete, and verifiable, and that the conduct of the trial is in compliance with the currently approved protocol/amendment(s), with GCP, and with applicable regulatory requirement(s):

- The NYU Human Research Protection Program may monitor the progress of the study. Monitoring will occur at the HRP's discretion on a random basis at any frequency it deems necessary to ensure compliance and study safety.
- Independent audits will not be conducted to ensure monitoring practices are performed consistently across all participating sites. This is a single-site study.
- Each clinical site will perform internal quality management of study conduct, data collection, documentation and completion. An individualized quality management plan will be developed to describe a site's quality management.

10 Statistical Considerations

10.1 Statistical and Analytical Plans (SAP)

There will not be a formal SAP.

10.2 Statistical Hypotheses

Primary endpoint. Exoskeletal support will increase RC in stroke participants. Paired t-test comparing RC from baseline to loading blocks.

Primary endpoint. Exoskeletal support will decrease MC in stroke participants. Paired t-test comparing MC from baseline to loading blocks.

Secondary endpoint. There will be an association between change in RC (or MC) and CST lesion load. Independent linear regressions (RC vs. CSTLL and MC vs. CSTLL).

Secondary endpoint. RC values in stroke participants will be less than RC values in healthy controls during baseline blocks (t-test). MC values in stroke participants will be greater than MC values in healthy controls during baseline blocks (t-test).

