3.2 Secondary Objectives

To establish corticospinal tract lesion load as a correlate of kinematic and neuromuscular responsiveness to exoskeletal support. We do this by associating the change in RC (or MC) with the variance in overlap between the lesion and the corticospinal tract (CST lesion load) using clinical standard of care MRI scans.

4 Study Design and Endpoints

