4.2.2 Secondary Study Endpoints

The secondary endpoint will be a significant relationship between the change in MC (% decrease in MC) and CSTLL with an R^2 value greater than 0.4 (Brunfeldt et al., *in review*).

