10.4 Description of Statistical Methods

10.4.1 General Approach

This study is a repeated measures cohort design. Two groups of participants (stroke, healthy control) will perform a reaching task with and without an exoskeleton device. Primary endpoint measures will be compared within-subject to assess the effects of exoskeleton loading on coordination (kinematic: RC and muscular: MC). A between-subjects analysis will be performed to assess differences in arm control between stroke and healthy control participants.

- For descriptive statistics, we will use ranges, means, and standard deviation as appropriate. For example individual ages will be reported and further summarized with mean and standard deviation.
- For inferential statistics, we will perform two-tailed paired- and unpaired t-tests and ANOVA where appropriate. Statistical significance will be assessed at the Type-I error less than $p = 0.05$ level. See Section 10.4.2.
- Covariates will not be pre-specified
- Statistical test assumptions will be analyzed following data collection. Appropriate adjustments (e.g., normality) will be performed, such as transformation or the use of non-parametric tests.

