10.4.3 Analysis of the Secondary Endpoint(s)

Secondary study objective (Motor performance vs. CST lesion load)

- We first perform linear regressions to assess the relationship between lesion load and Upper Extremity Fugl-Meyer (UE-FM). Coefficient of determination (R^2) values ranging from 0.2 to 0.7 have been previously reported (Cassidy et al., 2018; Feng et al., 2015; Lin et al., 2019; Zhu et al., 2010).
- We regress lesion load into the change in RC (ΔRC), change in MC (ΔMC), and tradeoff slope. Any motor performance measures that fail to achieve R^2 values greater than 0.2 when regressed to CST lesion load will be discarded from further analysis.

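### The secondary lesion-load endpoint has two conflicting success rules: MC alone with R² above 0.4 (synopsis, 4.2.2), or RC or MC at 0.05 (3.2, 10.2)

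*Combined protocol and SAP*

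**What the plan says.** **MC only.** Section 4.2.2 states: "The secondary endpoint will be a significant relationship between the change in MC (% decrease in MC) and CSTLL". The sentence goes on to require R² above 0.4, and the synopsis repeats the rule. The sample-size text in 10.5 takes its effect size for the secondary objective from the lesion-load relationship with change in MC, and from nothing else.

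**RC or MC.** The secondary objective in 3.2 reads "We do this by associating the change in RC (or MC) with the variance in overlap between the lesion and the corticospinal tract". Section 10.2, under the label of a secondary endpoint, gives the hypothesis and its analysis as "There will be an association between change in RC (or MC) and CST lesion load. Independent linear regressions (RC vs. CSTLL and MC vs. CSTLL". Neither section carries an R² threshold.

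**A third measure and a third threshold.** Section 10.4.3 says "We regress lesion load into the change in RC (ΔRC), change in MC (ΔMC), and tradeoff slope", followed by "Any motor performance measures that fail to achieve R^2 values greater than 0.2 when regressed to CST lesion load will be discarded" from further analysis.

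**Error level.** Section 10.4.1 says "Statistical significance will be assessed at the Type-I error less than $p = 0.05$ level". No adjustment or test order is given. Section 4.2.3 lists no exploratory endpoints, and 10.1 says there will be no formal SAP, so no later document is planned to settle the matter.

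**The concern.** The two rules can give opposite answers on the same data. If the MC regression fails and the RC regression gives p just below 0.05, section 10.2 can be read as success and 4.2.2 cannot. They can also disagree on MC itself: with 12 participants, an R² between about 0.33 and 0.40 is significant at 0.05 but misses the 4.2.2 threshold.

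The choice between the rules should be fixed before data are seen. The lesion-load association is likely to be a main finding: section 2.2.1 reports that the previous study in 14 stroke participants found no group-level change in RC or MC, but did find differences related to lesion overlap. The study is unmasked (10.6.1), lesions are traced by hand (4.1), and one investigator both collects and analyses the data (16.1). An open choice of success rule would let the result select the rule.

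**Working it through.** **Inputs.** N = 12 stroke participants, R² = 0.4648, f² = 0.7–0.9, power 0.8 and alpha 0.05 (10.5); R² above 0.4 (4.2.2); R² above 0.2 (10.4.3); 0.05 per test (10.4.1). The correlation between the outcomes is not in the documents and is assumed to range from 0 to 0.9.

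**1. The plan's own figure.** f² = 0.4648 / (1 − 0.4648) = 0.868. For a one-predictor regression, power comes from the noncentral F distribution with 1 and N − 2 degrees of freedom and noncentrality f² × N.

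| f² | Smallest N for 80% power | Power at that N |
|---|---|---|
| 0.7 | 14 | 81.9% |
| 0.868 | 12 | 82.8% |
| 0.9 | 12 | 84.1% |

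The stated 12–14 participants is reproduced, for one regression tested at 0.05.

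**2. Chance of passing with no true association, MC alone (4.2.2).** F = [R² / (1 − R²)] × (N − 2). At R² = 0.4 and N = 12, F = (0.4 / 0.6) × 10 = 6.67 on 1 and 10 df, so p = 0.027. Significance at 0.05 already requires R² above 0.332, so the R² condition is the binding one and the rule is passed 2.7% of the time.

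**3. RC or MC at 0.05 (10.2 read as either/or), and with tradeoff slope as a third route.** With independent outcomes the chance of at least one p below 0.05 is 1 − 0.95² = 9.75% for two tests and 1 − 0.95³ = 14.3% for three. For correlated outcomes it was simulated: 400,000 null datasets per setting, N = 12, one normal predictor, normal outcomes with a common correlation.

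| Correlation between outcomes | RC or MC | RC, MC or tradeoff slope |
|---|---|---|
| 0 | 9.8% | 14.2% |
| 0.5 | 9.2% | 12.9% |
| 0.8 | 8.0% | 10.3% |
| 0.9 | 7.2% | 8.7% |

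**4. If R² above 0.4 were required of every measure.** With independent outcomes: 1 − (1 − 0.0273)² = 5.4% for two and 1 − (1 − 0.0273)³ = 8.0% for three.

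**5. The 10.4.3 screen.** At N = 12, R² = 0.2 gives F = (0.2 / 0.8) × 10 = 2.5 and p = 0.145. A measure unrelated to lesion load therefore survives the screen 14.5% of the time.

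**The case against.** The best defence is that the endpoint is already fixed. The synopsis and 4.2.2 agree, 10.5 follows them, and under that rule the error rate is below 5%. A reader might infer that the plan as a whole runs an 8–14% risk instead of 5%. The documents do not support that, because it treats 10.2 as the operative rule and sets 4.2.2 aside. This part of the defence stands.

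Second, the alternative wording can be taken as shorthand for two separate hypotheses. Section 3.2 speaks of both kinematic and neuromuscular responsiveness, 10.2 lists two regressions joined by *and*, and no section says that either one suffices. On that reading each claim carries its own 5%. This is fair, and it makes the 7–10% conditional on the either/or reading. It does not remove the problem, because the objective then has two tests, no statement of which decides it, and still no match with 4.2.2.

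Third, a reader might infer from the empty exploratory section that tradeoff slope has secondary status. That does not follow: it is absent from the objective, the endpoint, the hypotheses and the outcome list in 10.3, and appears only in 10.4.3. The 9–14% is therefore an upper case. Nor should the baseline stroke-versus-control t-tests in 10.2 be added to the family. They test a different hypothesis and cannot produce a false lesion-load association.

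Last, this is a secondary endpoint in a 24-person pilot, where formal adjustment is largely a matter of preference. That limits the severity, but a contradiction about what counts as success remains.

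**Conclusion.** The concern holds as an internal contradiction about the success rule. With no true association and N = 12, the 4.2.2 rule is passed about 2.7% of the time. The 10.2 wording, read as either/or, is passed about 7–10% of the time, roughly 2.6 to 3.6 times as often (7.2 / 2.73 to 9.75 / 2.73). The rate reaches about 9–14% only if tradeoff slope also counts as success.

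These figures assume normal data, one predictor per regression, 12 analysed stroke participants and outcome correlations of 0 to 0.9. Section 10.5 cites a partial R², so the documents do not show whether the regression behind it contained other terms. The one-predictor calculation does reproduce the stated sample size. The point is worth correcting before analysis, but it does not threaten the primary objectives.

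**What to change.** - **10.2:** state that the regression of change in MC on CST lesion load, judged by the 4.2.2 rule (p below 0.05 and R² above 0.4), alone decides the secondary lesion-load objective.
- **3.2:** make the neuromuscular (MC) association the deciding one and call the kinematic (RC) association exploratory, so that both halves of the objective have a stated role.
- **4.2.3:** replace the empty entry with the change-in-RC and tradeoff-slope regressions, reported with confidence intervals and no success claim.
- **10.4.3:** state that passing the R² above 0.2 screen is not a success criterion.
- **Baseline t-tests in 10.2:** no change needed.

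This is wording only and follows the choice already made in the synopsis, 4.2.2 and 10.5. The cost is that a significant RC or tradeoff-slope regression could no longer be presented as meeting the secondary objective.

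The sponsor should also know that the R² condition in 4.2.2 has its own price: if the true R² is 0.4648, the chance of passing at N = 12 is 73.2%, against 82.8% for p below 0.05 alone. That follows from the existing endpoint, not from this change.

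Keeping several routes to success with a Bonferroni correction would also control the error. At N = 12 and R² = 0.4648, power on p alone would then fall from 82.8% to 71.7% (two tests at 0.025) or 64.3% (three at 0.0167), and 80% power would need 14 or 16 stroke participants.
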